1. INTRODUCTION

The purpose of this reporting and analysis plan (RAP) is to describe the analyses of Group 1 to be included in the Clinical Study Report for Protocol:

Revision Chronology:		
2016N281575_00	2016-AUG-22	Original
2016N281575_01	2016-OCT-10	Section 6.2: Inclusion of information on CE marking.
2016N281575_02	2018-JAN-04	Update to PK collection procedures and implementation of in-stream PK data analysis. Update to location of Secondary Medical Monitor contact information.
2016N281575_03	2018-MAY-30	Modification to informal interim and Group 2 analysis plans.

2. SUMMARY OF KEY PROTOCOL INFORMATION

2.1. Changes to the Protocol Defined Statistical Analysis Plan

Changes from the originally planned statistical analysis specified in the protocol are outlined in [Table 1](#).

Table 1 Changes to Protocol Defined Analysis Plan

Protocol	Reporting & Analysis Plan	
Statistical Analysis Plan	Statistical Analysis Plan	Rationale for Changes

 To compare pharmacokinetics of IH oxytocin to 10 I.U. IM oxytocin in women in TSL. 	
 To produce summary statistics for IH and IM Oxytocin 	
 Due to sparse PK concentration available for IM and IH Oxytocin a formal statistical analysis comparison is not possible; summary statistics will be presented instead.

 To characterize the pharmacokinetics of single doses of IH oxytocin and 10 International Units (I.U.) IM oxytocin in women in TSL. 	
 To produce individual plasma concentration-time plots and summary statistics for PK parameters : Maximum observed plasma concentration (C_{max}), Observed plasma concentrations at 10 minutes (min) postdose (C_{p10}), Observed plasma concentrations at 20 min post-dose (C_{p20}), Observed plasma concentrations at 30 min post-dose (C_{p30}), Time to C_{max} (t_{max}), Area under 	
 As only sparse PK concentration is available for IM and IH Oxytocin PK parameters will be derived wherever data permit. Terminal Phase half-life (t_{1/2}) will not be calculated. AUC(0-3h) will not be calculated instead AUC(0-t) and time of last quantifiable concentration will be computed.

Protocol	Reporting & Analysis Plan	
Statistical Analysis Plan	Statistical Analysis Plan	Rationale for Changes
	concentration-time curve from time zero to the time of the last quantifiable concentration (AUC(0-t)), as data permit. Terminal Phase half-life (t _{1/2}) will not be calculated	

 To compare pharmacokinetics of IH oxytocin between Group 1 and Group 2 	
 No statistical comparison will be done 	
 As only sparse PK concentration is available for IH Oxytocin in Group 1 as compared to Group 2, a statistical comparison will not be reported.

 All Subjects Population 	
 All Subjects population label changed to Safety population. 	
 To be compliant with the new RAP template

 Enrolled Population (Defined as all subjects who were enrolled for the trial irrespective of whether they were randomized or not and for whom a record exists on the study database. This population will be used for summarizing screening failure reasons. 	
 All participants who passed screening and entered the study including randomized participants and run in failures 
Note: Screening failures (who never passed screening even if rescreened) and participants screened but never enrolled into the study (Reserve, Not Used) are excluded from the Enrolled population as they did not enter the study.
	
 To be compliant with the new RAP template

2.2. Study Objective(s) and Endpoint(s)

Group 1 – Women in Third Stage of Labour (TSL)op

Objectives	Endpoints
Primary Objectives	Primary Endpoints

 To characterize the pharmacokinetics of single doses of IH oxytocin and 10 International Units (I.U.) IM oxytocin in women in TSL. 	
 Plasma concentration time profile for IH oxytocin and 10 I.U. IM oxytocin. PK parameters: Maximum observed plasma concentration (C_{max}), Observed plasma concentrations at 10 minutes (min) postdose (C_{p10}), Observed plasma concentrations at 20 min post-dose (C_{p20}), Observed plasma concentrations at 30 min post-dose (C_{p30}), Time to C_{max} (t_{max}), Area under concentration-time curve (AUC), and Terminal phase half-life (t_{1/2}) will be calculated as data permit.
Secondary Objectives	Secondary Endpoints

 To evaluate the safety and tolerability of inhaled oxytocin. 	
 General safety parameters: adverse events (AE); absolute values and changes over time of vital signs (blood pressure, heart rate, respiratory rate, temperature).

Objectives	Endpoints

 To compare pharmacokinetics of IH oxytocin to 10 I.U. IM oxytocin in women in TSL. 	
 C_{max}, C_{p10}, C_{p20}, C_{p30}, Area under the concentration-time curve from time zero (pre-dose) to three hours (h) (AUC[0-3h]) will be compared as data permit.
Exploratory Objectives	Exploratory Endpoints

 Pharmacodynamic effect of IH oxytocin and 10 I.U. IM oxytocin in women in TSL. 	
 Pre and post-delivery haemoglobin

 Participant feedback regarding ease of use, instructions, and perceived ability of patients to use the ROTAHALER. 	
 Questionnaire results from participants.

[figure not shown]
[figure not shown]
Group 2 – Non-pregnant, non-lactating females of child bearing potential

Objectives	Endpoints
Primary Objectives	Primary Endpoints

 To evaluate the safety and tolerability of IH and IV Oxytocin 	
 General safety parameters: adverse events; absolute values and changes over time of vital signs (blood pressure, heart rate) and 12-lead electrocardiogram (ECG) parameters (PR, QRS, QT, Corrected QT interval [QTc] intervals) from pre-dose values. Specific respiratory safety parameters: adverse respiratory events as monitored by spirometry including Forced expiratory volume at 1 minute (FEV1.0), respiratory rate, and pulse oximetry.

 To characterize the pharmacokinetics of single doses of IH oxytocin and 5 I.U. IV oxytocin. 	
 Plasma concentration time profile for IH oxytocin and 5 I.U. IV oxytocin. PK parameters: C_{max}, C_{p10}, C_{p20}, C_{p30}, t_{max}, AUC, Plasma clearance (CL), volume of distribution and t_{1/2} will be calculated as data permit.
Exploratory Objectives	Exploratory Endpoints

 To evaluate endogenous plasma oxytocin concentrations in non-pregnant females in the presence and absence of the combined oral contraceptive. 	
 Pre-dose plasma concentrations of oxytocin.

 To compare the IH pharmacokinetics of oxytocin between Cohort A (subjects on combined oral contraceptive) and Cohort B (subjects using a non-hormonal form of contraception). 	
 C_{p10}, C_{p20}, C_{p30}, C_{max}, AUC(0-3h), Area under the concentration time curve from time zero to infinity (AUC[0-∞]) and t_{1/2}, will be compared as data permit.

 To compare the IV pharmacokinetics of oxytocin between Cohort A and Cohort B. 	
 C_{max}, AUC, t_{1/2}, CL and Volume of distribution (VOD) will be compared as data permit.

Groups 1 and 2 – Women in TSL and Non-pregnant, non-lactating females of child bearing potential

Objectives	Endpoints
Primary Objectives	Primary Endpoints

To compare pharmacokinetics of IH oxytocin between Group 1 and Group 2	
Cp10, Cp20, Cp30, Cmax, AUC(0-3h) AUC(0-∞), and t1/2 will be compared as data permit.

2.3. Study Design

Overview of Study Design and Key Features	

Group 1 – Women in TSL
  
Group 2 – Non-pregnant, non-lactating females of child bearing potential
 	
Design Features	
 Group 1: This is an open-label, randomized, single dose study enrolling women in the third stage of labour who will receive either IH or IM oxytocin Group 2: This is an open-label, randomized, two dosing, cross over study enrolling healthy, non-pregnant, non-lactating female subjects of childbearing potential who will receive IH oxytocin at one dosing session and IV oxytocin at the other dosing session. It will be divided into two cohorts: Cohort A will enrol women on a combined oral contraceptive. Cohort B will enrol women who are not using a hormonal form of contraceptive.
Dosing	
 Group 1: Subjects will receive 400 mcg IH oxytocin or 10 I.U. IM oxytocin in one dosing session. Follow Up 1 within approximately 24 hours post dose. Follow Up 2 at least 7 days and no greater than 14 days after study drug administration. Total duration: Screening after 18th week of pregnancy (i.e. within 168 days of 1 dosing session) + follow up of 7 - 14 days = approximately 183 days Group 2: Subjects will receive 400 mcg IH oxytocin and 5 I.U. IV oxytocin in two dosing sessions. Follow Up will take place at least 7 days and no greater than 21 days after last study drug administration. Total duration: Screening within 28 days of dosing session 1 + 2 dosing sessions with a maximum of 14 days between dosing + follow-up of 7 – 21 days = 64 days
Time & Events	
 [Refer to Appendix 2: Schedule of Activities]
Treatment Assignment	
 Group 1: Subjects will be randomised to receive one of the following study treatments: A: 400 mcg IH oxytocin B: 10 I.U. IM oxytocin Group 2: Subjects will receive both of the following study treatments over the course

Overview of Study Design and Key Features	
	of two dosing sessions: C: 400 mcg IH oxytocin D: 5 I.U. IV oxytocin
Interim Analysis	
 No formal Interim Analysis are planned, however, PK samples will be analysed and preliminary PK parameters derived following completion of approximately 5 women on each treatment group: 400 mcg IH and 10 I.U. IM to women in TSL (Group 1) and 400 mcg IH to non-pregnant women on the combined oral contraceptive (Group 2 Cohort A), in order to assess if dose escalation is required.

2.4. Statistical Hypotheses / Statistical Analyses

No formal hypotheses will be tested.

For IH and IM oxytocin, summary statistics will be produced separately for IH Oxytocin and IM Oxytocin. Due to sparse PK concentrations, it is not possible to include a formal statistical analysis to compare IH and IM Oxytocin. PK parameters will be derived as data permit. Individual plots, listings and summary tables will be produced for available PK concentration data. Only listings and summary tables will be produced for PK Parameter data.

3. PLANNED ANALYSES: GROUP 1

3.1. Interim Analyses: Group 1

No formal Interim Analysis are planned, however, PK samples will be analysed and preliminary PK parameters derived following completion of approximately 5 women on each treatment group: 400 mcg IH and 10 I.U. IM to women in TSL (Group 1) and 400 mcg IH to non-pregnant women on the combined oral contraceptive (Group 2 Cohort A), in order to assess if dose escalation is required.

Due to sparse PK concentration-time data available following administration of IH and IM oxytocin to women in TSL, only concentration time plots were presented at the interim analysis. The Study has been terminated early due the unanticipated inability to be able to quantify plasma oxytocin using a selective and sensitive (LLQ 2pg/mL) analytical assay due to low oxytocin concentrations (<2pg/mL) in the majority of samples collected from women in Third Stage Labour (TSL), following either IM or IH administration. Therefore, the Primary objective of the study to characterise the PK of single doses of IH and IM oxytocin in women in TSL, cannot be met, and the study is being terminated

3.2. Final Analyses

The final planned primary analyses for Group 1 will be performed after the completion of the following sequential steps:

1. All participants who had enrolled into the study prior to the termination of the study as defined in the protocol will be part of final analysis.
2. All required database cleaning activities have been completed for group 1 and final database release (DBR) and database freeze (DBF) for group 1 has been declared by Data Management.
3. All criteria for unblinding the randomization codes for group 1 have been met.
4. Randomization codes for group 1 have been distributed according to RandAll NG procedures.

4. ANALYSIS POPULATIONS

Population	Definition / Criteria	Analyses Evaluated
Screened	
 All participants who were screened for eligibility 	
 Screen Failures
Enrolled	
 All participants who passed screening and entered the study including randomized participants and run in failures 
Note: Screening failures (who never passed screening even if rescreened) and participants screened but never enrolled into the study (Reserve, Not Used) are excluded from the Enrolled population as they did not enter the study.
	
 Study Population
Safety	
 Comprise of subjects who receive at least one dose of study medication. This population will be used for the study population and safety displays. 
Note: This population will be based on the treatment the participants actually received
	
 Study Population Safety
Pharmacokinetic (PK)	
 Subjects in the 'Safety' population for whom a pharmacokinetic sample was obtained and analysed. PK population will be the population for reporting PK data. 	
 PK

Refer to [Appendix 10](#): List of Data Displays which details the population used for each display.

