IH/IM	AUC(0-t)	Area under the concentration-time curve from time zero to the time of the last quantifiable concentration (C(t)) will be calculated using the linear trapezoidal rule for each incremental trapezoid and the log trapezoidal rule for each decremental trapezoid.
IH/IM	t _{last}	Time of last quantifiable concentration

At least 2 quantifiable (3 including time 0 where NQ values at time zero will be set to 0) values per profile are required to calculate the AUC(0-t). For profiles with less than 2 quantifiable values, AUC(0-t) will be coded with NC in the PKPar file.

8.1.2. Summary Measure: Group 1

Pharmacokinetic concentration data will be presented in graphical and/or tabular form and will be summarized descriptively by IH oxytocin and IM Oxytocin.

The conversion factor to normalise IM doses is 1 IU = 1.7 mcg oxytocin

As a large number of PK parameter values will be reported as Non Calculable (NC: PK parameter cannot be derived due to the presence of non-quantifiable data) then the PK parameter will be summarised by following measures

- number of subjects with non-missing observations, n, (includes those reported as NC)
- number of subjects for whom parameter cannot be derived because of NQ concentrations, n*, (reported as NC)
- median, minimum and maximum

In addition a frequency table of the number of subjects with all concentrations NQ and the number of subjects with one, or 2 or more measurable concentrations will be produced.

8.1.3. Population of Interest : Group 1

The primary pharmacokinetic analyses will be based on the Pharmacokinetic population, unless otherwise specified.

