10.2.1.2. Time & Events - Main Phase Procedures

Group 1

Procedure	Pre-dose	Time post dose										
		3 min	5 min	10 min	15 min	20 min	30 min	1 hr	2 hr	2.5 hr	3 hr	4 hr
Vital signs ¹							X		X			
Pharmacokinetic blood sample	X ²	X	X	X	X	X	X	X	X	X	X	X
Prior medication review	X											
Concomitant medication review		----- continuous review -----										
AE review		----- continuous review -----										
SAE Review		----- continuous review -----										
Device Acceptability Questionnaire ³												X
Full Blood Count	X											X

1. Includes blood pressure, heart rate, temperature, respiratory rate
2. Predose PK sample to be taken immediately prior to administration of study treatment
3. Only to be administered when randomized to IH oxytocin

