10.10.5. Pharmacokinetic Tables

Pharmacokinetic Tables					
No.	Population	IDSL / Example Shell	Title	Programming Notes	Deliverable [Priority]
PK Concentration Data					
2.6.	PK	pkct1	Summary of Plasma Concentration-time Data	Page by subjects before study restart, subjects after restart and all subjects together.	SAC
2.7.	PK	PK_T1	Summary of Derived Plasma Pharmacokinetic Parameters (untransformed data)	Page by subjects before study restart, subjects after restart and all subjects together. This will be an overall summary and will not be displayed by timepoints.	SAC
2.8.	PK	PK_T2	Summary of Number and Percentage of Subjects with Measurable Concentrations	Page by subjects before study restart, subjects after restart and all subjects together. This will be an overall summary and will not be displayed by timepoints.	SAC

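### Group 1: the per-woman count of measurable concentrations (Table 2.8) and Cmax are not limited to post-dose samples

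*SAP*

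**What the plan says.** The SAP holds two plans, one per group. This point concerns the Group 1 plan.

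- **Population (section 4).** The PK population is "Subjects in the 'Safety' population for whom a pharmacokinetic sample was obtained and analysed", and "PK population will be the population for reporting PK data". Section 4.1 adds that protocol deviations do not change the populations used for the endpoints.
- **Schedule (section 10.2.1.2).** PK blood is drawn before dosing and at 11 post-dose times from 3 minutes to 4 hours. The footnote reads "Predose PK sample to be taken immediately prior to administration of study treatment".
- **Count (section 8.1.2).** The plan promises a "frequency table of the number of subjects with all concentrations NQ and the number of subjects with one, or 2 or more measurable concentrations". This becomes Table 2.8, whose programming note in section 10.10.5 says "This will be an overall summary and will not be displayed by timepoints".
- **Cmax (section 8.1.1.2).** It is the highest observed concentration, read directly from the concentration-time data. No post-dose condition is given.
- **AUC(0-t) (end of section 8.1.1.2).** "At least 2 quantifiable (3 including time 0 where NQ values at time zero will be set to 0) values per profile are required". This is the only minimum-data rule.
- **Reason for stopping (section 3.1).** Oxytocin was below 2 pg/mL "in the majority of samples collected from women in Third Stage Labour (TSL), following either IM or IH administration".

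**The concern.** The finding that ended the study concerns samples taken after dosing. Table 2.8 is the only planned display that says, woman by woman, whether oxytocin was quantifiable, but its categories cover every sample she gave. A measurable pre-dose value is not evidence of exposure to the study dose, yet it can move a woman out of the all-NQ category, or from one measurable value to two or more. This needs no missed samples; it can happen in a woman with all 12.

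The plan also gives no count of samples behind each category. A woman with one NQ sample and a woman with twelve both appear as all NQ, though the second tells far more. Tables 2.7 and 2.8 are paged by before and after study restart, and the revision history records that amendment 2 changed PK collection procedures. If the number of samples per woman differed between those pages, the percentages would partly reflect sampling effort.

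The same openness affects Cmax in Table 2.7: a woman quantifiable only before dosing could contribute that value.

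**Working it through.** The plan states no figure that depends on this point, so there is none to reproduce. The check has two parts.

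**1. Literal application of the rules**

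| Woman | Table 2.8 category as written | Post-dose samples only |
|---|---|---|
| Pre-dose measurable, 11 post-dose NQ | one | all NQ |
| Pre-dose measurable, 1 of 11 post-dose measurable | 2 or more | one |
| One NQ sample in total | all NQ | all NQ if post-dose (1 sample); outside the denominator if pre-dose |
| Twelve NQ samples | all NQ | all NQ (11 samples) |

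In the first row, the rule for Cmax returns the pre-dose value. The AUC(0-t) rule gives no value there, because fewer than two concentrations are quantifiable.

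**2. Illustration of size**

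Inputs from the plan: 12 scheduled samples, 1 pre-dose and 11 post-dose. Assumed, because the plan gives no rates: *p*, the chance that a post-dose sample is quantifiable; *q*, the chance that the pre-dose sample is; samples independent.

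Counting the pre-dose sample changes the category of a fully sampled woman when that sample is quantifiable and 0 or 1 of the 11 post-dose samples are:

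P(change) = q × [(1−p)^11 + 11·p·(1−p)^10]

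- p = 0.10, q = 0.10: 0.10 × (0.3138 + 0.3835) = 0.070. About 0.031 of this moves from all NQ to one, and 0.038 from one to 2 or more.
- p = 0.10, q = 0.30: 0.30 × 0.6974 = 0.209.
- p = 0.30, q = 0.05: 0.05 × (0.0198 + 0.0932) = 0.006.
- p = 0.05, q = 0.30: 0.30 × (0.5688 + 0.3293) = 0.269.

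With *p* and *q* each between 0.05 and 0.30, the range is about 0.006 to 0.27.

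For the number of samples, P(all NQ | k samples) = (1−p)^k, with the same *p* for every sample:

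| p | 1 sample | 12 samples |
|---|---|---|
| 0.10 | 0.90 | 0.28 |
| 0.20 | 0.80 | 0.07 |
| 0.30 | 0.70 | 0.01 |

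**Weight of one woman.** Final arm sizes are not stated. With 5 per arm (the trigger for the informal interim look) one woman is 1/5 = 20 percentage points; with 24 (a placeholder in shell PK_T1) she is 1/24 = 4.2 points. Neither figure is an actual denominator.

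**The case against.** Several objections carry weight.

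- **Shell not visible.** In the text at hand, the shell for Table 2.8 (PK_T2, Appendix 11) stops at its title. A row or footnote setting pre-dose values apart may exist. Section 8.1.1.2 also defers to working practices that are not shown and may restrict Cmax. This stands: the point rests on the visible text.
- **Other displays show time.** Table 2.6, Figure 2.8 and Listing 52 let a reader separate pre-dose from post-dose values. This stands and limits the harm, but none of them is a per-woman summary.
- **The termination finding is at sample level.** It refers to most samples and had been reached before these tables. A reader might infer that Table 2.8 could overturn it; nothing in the plan supports that.
- **The pre-dose-only woman is hypothetical.** With 11 post-dose samples scheduled, she is probably rare. A reader might infer that she would enter n and n* in Table 2.7 and receive an imputed Cmax. The text does not clearly say so: section 8.1.2 reserves n* for parameters that NQ concentrations make underivable, and her Cmax would be missing because nothing was sampled. The imputation stands only in a mock-shell footnote with template values (half the LLQ given as 5 pg/mL, against an LLQ of 2 pg/mL in section 3.1).
- **Comparison of arms.** The plan drops the formal IH–IM comparison, both arms share one schedule, and no differential sampling is documented. A claim that the IH and IM percentages are not comparable goes too far.

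**Conclusion.** The point holds for Group 1 in a limited form. As visibly written, Table 2.8 does not isolate quantifiability after dosing, does not show how many samples lie behind each category, and leaves Cmax open to a pre-dose value.

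The size is modest. No test, sample size or stated figure changes. The probabilities above rest on assumed rates and independence, and show only that the effect can range from negligible to more than one woman in five.

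A reader might go further and conclude that the PK population itself is wrongly defined in both groups. The documents do not support that. In Group 2, pre-dose oxytocin is an exploratory endpoint analysed on the PK population (Group 2 plan, sections 8.3.1 to 8.3.3), so a rule that any analysed sample qualifies suits it. Group 2 also has no table of measurable counts.

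**What to change.** In Group 1 only:

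1. State in section 8.1.2 and the Table 2.8 programming note that the three categories use post-dose samples only.
2. Add a separate row for whether the pre-dose sample was quantifiable, yes or no.
3. Report the number of post-dose samples analysed per woman.
4. State in section 8.1.1.2 that Cmax is taken from post-dose samples.
5. Use PK-population women with at least one analysed post-dose sample as the denominator for Tables 2.7 and 2.8.

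Leave the PK population definition as it is in both groups. If the PK_T2 shell already restricts the count, carry that wording into section 8.1.2.

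The cost is a few lines of text, a filter in two tables, and possibly a slightly smaller denominator. Women without a post-dose sample stay in the PK population and in Listing 52.
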